5.1.3. Intervention Group

The population will be the FAS defined in Section 4 for all the efficacy analysis, and the assigned treatment group for each participant will be used regardless of the actual treatment received.

All the safety analyses will be performed on safety analysis set, and by the actual treatment participants received regardless of the assigned treatment.

5.1.4. Visit Windows

Unless otherwise specified, nominal visits will be used for all by visit analyses. The study visits scheduled after randomization should occur at the time delineated in the Schedule of Activities as described in the protocol.

5.2. Participant Dispositions

Screened participants and the number of screen failures will be summarized overall in all enrolled participants.

The number of participants in the following disposition categories will be summarized in the main study period and LTE period by intervention group and overall:

- Participants randomized
- Participants who received study intervention
- Participants who completed the study
- Participants who discontinued study intervention
- Reasons for discontinuation of study intervention
- Participants who terminated study prematurely
- Reasons for termination of study

Listings of participants will be provided for the following categories:

- Participants who discontinued study intervention
- Participants who terminated study prematurely

5.3. Primary Endpoint Analysis

The primary endpoint is the change from baseline in mRSS at Week 24. This section outlines the definitions and analysis of this primary endpoint.

5.3.1. Definition of Endpoint

The mRSS is a validated physical examination method for estimating skin induration. It correlates with biopsy measures of skin thickness and reflects prognosis and visceral involvement, especially in early disease. It is scored on 0 (normal) to 3 (severe induration) ordinal scales over 17 body areas, with a maximum score of 51 and is used to categorize severity of SSc ([Khanna 2007](#)).

This assessment should be performed by a physician who is experienced and trained in skin scoring. To prevent interobserver variability, the same physician must perform skin scoring for the same participant throughout the entire study.

5.3.2. Estimands

1. Primary Estimand (Composite Estimand)

The primary estimand is defined as the following components:

Primary Trial Objective: to evaluate the efficacy of guselkumab in participants with SSc

Estimand Scientific Question of Interest: what is the efficacy, as is measured by change from baseline in mRSS at Week 24 for participants who are assigned to guselkumab versus placebo

Study Intervention:

- Experimental: guselkumab
- Control: placebo

Population: participants between 18 to 75 years (inclusive) with diagnosis of SSc according to ACR and EULAR 2013 criteria with a disease duration of ≤ 36 months (defined as time from first non-Raynaud phenomenon manifestation), and mRSS ≥ 10 to ≤ 22 units

Variable: change from baseline in mRSS at Week 24. Participants with an intercurrent event before Week 24 will have a zero change from baseline in the mRSS since the intercurrent event occurs, regardless of the observed data.

Summary measure (Population-level summary): difference in least-square means (LSMs) of change from baseline in mRSS at Week 24 between guselkumab vs placebo

Intercurrent events and their corresponding strategies:

Intercurrent Events	Strategy for Addressing Intercurrent Events and Its Description
A prohibited change in SSc medication (for details, see Appendix 11)	Composite Strategy: A participant with this intercurrent event is considered to have a zero change at and after the event occurred.
Discontinuation of study intervention due to lack of efficacy or an AE of Systemic Sclerosis	Composite Strategy: Same as above

2. Supplementary Estimand (Hypothetical Estimand)

This supplementary estimand will be used to complement the primary estimand. The components of the supplementary estimand are the same as those for the primary estimand with the exception of definitions in Variable and Intercurrent event strategies (**hypothetical strategy**), which are described as follows:

Variable: change from baseline in mRSS at Week 24. Participants with an intercurrent event before Week 24 will have their mRSS set to missing since the intercurrent event occurs.

Intercurrent events and their corresponding strategies:

Intercurrent Events	Strategy for Addressing Intercurrent Events and Its Description
A prohibited change in SSc medication (for details, see Appendix 11)	Hypothetical Strategy: A participant with this intercurrent event is considered to have missing data at and after the event occurred.
Discontinuation of study intervention due to lack of efficacy or an AE of Systemic Sclerosis	Hypothetical Strategy: Same as above

3. Supplementary Estimand (Treatment Policy Estimand)

In this estimand, the components are almost the same as those for the primary estimand with the exception of definitions in Variable and Intercurrent event strategies (treatment policy strategy), which are described as follows:

Variable: change from baseline in mRSS at Week 24

Intercurrent events and their corresponding strategies:

Intercurrent Events	Strategy for Addressing Intercurrent Events and Its Description
A prohibited change in SSc medication (for details, see Appendix 11)	Treatment Policy Strategy: The intercurrent event does not affect the outcome, and the data collected at and after the event will be used for analysis.
Discontinuation of study intervention due to lack of efficacy or an AE of Systemic Sclerosis	Treatment Policy Strategy: Same as above

5.3.3. Analysis Methods

The primary analysis will use a Mixed-Effect Model Repeated Measure (MMRM) model. Under the assumption of MAR, the missing data will be accounted for through correlation of repeated measures in the model.

The MMRM model includes treatment group, baseline mRSS, stratification factors (presence of ILD [yes, no] and baseline anti-topoisomerase I antibody status [positive, negative]), visit, treatment group by visit interaction, and baseline mRSS by visit interaction as fixed effects. Stratification factor of baseline mRSS is not included as baseline mRSS is already addressed in the model as a continuous covariate. Treatment effects will be estimated based on least-square means (LSMs) of the differences. The p-values for the LSM differences along with the 2-sided 80% and 95% CIs will be presented. The degree of freedom will be calculated as the error degrees of freedom for the model minus the number of extra random effects estimated.

An unstructured covariance matrix for repeated measures within a participant will be used. In case of lack of convergence, empirical structured covariances will be used in the following order until convergence is reached: 1) Toeplitz 2) first order Autoregressive Moving Average. If the normality assumption is in question, an appropriate transformation will be used.

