3. SAMPLE SIZE DETERMINATION

There is lack of positive placebo-controlled trials in dcSSc.

Taking into account the following 4 Phase 2/3 placebo-controlled trials (see [Table 2](#)) in SSc with mRSS results reported in the ClinicalTrials.gov registry, a reasonable estimate of the standard deviation (SD) to be used in the sample size calculation of this study has been taken as 8.0.

Table 2: Standard deviations of mRSS in Referenced Phase 2/3 Placebo-controlled Trials in SSc

Trial	Treatment group		Placebo group	
	N	Estimated SD	N	Estimated SD
A Double-Blind, Randomised, Placebo-controlled Trial Evaluating Efficacy and Safety of Oral Nintedanib Treatment for at Least 52 Weeks in Patients With Systemic Sclerosis Associated Interstitial Lung Disease (SSc-ILD) (NCT02597933)	288	4.582	288	4.412
A Phase 3, Multicenter, Randomized, Double-Blind, Placebo-Controlled, Parallel-Group Study to Assess the Efficacy and Safety of Tocilizumab Versus Placebo in Patients With Systemic Sclerosis (NCT02453256)	104	8.169	106	8.142
A Phase 2/3, Multicenter, Randomized, Double-blind, Placebo-controlled Study To Assess The Efficacy And Safety Of Tocilizumab Versus Placebo In Patients With Systemic Sclerosis (NCT01532869)	43	8.266	41	8.933

Trial	Treatment group		Placebo group	
	N	Estimated SD	N	Estimated SD
A Phase 2 Study to Evaluate Subcutaneous Abatacept vs. Placebo in Diffuse Cutaneous Systemic Sclerosis- a Double-blind, Placebo-controlled, Randomized Controlled Trial (NCT02161406)	44	7.562	44	7.562

[Khanna et al \(2006\)](#) revealed that a 95% confidence interval (CI) of [-4.7, -1.7] in mRSS change from baseline to 6 months was considered a clinically meaningful change. The lower bound of this 95% CI, -4.7, has been taken as the expected treatment difference in the sample size calculation of this study, assuming guselkumab can achieve a clinically meaningful change in most of guselkumab-treated participants.

Assuming an SD of 8 points, an 80% power at a 2-sided significance level of 0.20, with a 1:1 randomization ratio, to detect a treatment effect of -4.7 points, a total of at least 54 participants will be required.

Allowing for up to 2 participants randomized but without postbaseline efficacy assessments, approximately 56 (28 each) randomized participants are planned. In order to evaluate the interobserver and intraobserver variability of the mRSS to support Phase 3 planning, it is desirable for each center to randomize 3 participants at least.

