5.1.1. Level of Significance

As a PoC study, a 2-sided alpha of 0.2 is allocated for all hypothesis testing throughout the study. As the reference of the internal GO/NO-GO decision making, 95% CIs as well as 80% CIs will be provided for primary endpoint analysis and secondary endpoint analysis.

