5.3.5. Sensitivity Analyses

If at least one data through Week 24 is missing and p-value is <0.2 with the primary analysis, a sensitivity analysis for primary estimand (Composite Estimand) will be performed, using multiple imputation.

Step #1: Utilize a Markov Chain Monte Carlo (MCMC) approach to impute intermediate (nonmonotone) missing data and convert the dataset into a monotone missing data pattern. One hundred monotone datasets will be imputed using the seed 12345, by treatment group.

Step #2: After imputing nonmonotone data, the remaining missing value will be imputed using the PROC MI monotone regression procedure. This approach imputes missing data in a sequential manner, for each time point, a regression model based on all available data at this timepoint (either observed or imputed) is fitted and used to impute values still missing at this timepoint. The ancillary variable included in the model will be treatment group, the stratification factors, and the mRSS scores by visit. The seed is 54321. In this way, one thousand complete datasets are generated.

Step #3: Analyze each of the 100 imputed datasets using the same model specified for the primary analysis and the results will be combined using the PROC MIANALYZE procedure.

The tipping point analysis will be implemented to assess the robustness of conclusions. A constant delta is added or subtracted to the imputed data in the direction of lack of efficacy for guselkumab and in the direction of improvement for placebo. A range of evenly spaced deltas will be used to adjust imputed values in the guselkumab and placebo group independently in order to produce a grid of delta adjustments to missing values in both groups. The size of the deltas will be chosen pragmatically, so that adjustments that lead to p-value ≥ 0.2 are encompassed in the grid. In particular, assuming MAR on placebo, ie, no delta adjustment, an adjustment on the guselkumab arm that just tips the analysis into p-value ≥ 0.2 will be included.

For each pair of delta adjustments, the point estimate of treatment effect, and corresponding p-value combined from results from 1000 adjusted datasets through the PROC MIANALYZE procedures will be presented.

Ukyo and Noma proposed the permutation-based inference methods for the analyses using MMRM that is considered to be more appropriate under small sample settings ([Ukyo 2019](#)). Their method will be applied to examine the robustness of the primary analysis result.

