Step #1: Permute the treatment group indicator of the mRSS dataset. The seed is defined as 127.

Step #2: Calculate the t -statistics ($T^{(b)}(\beta_1^{null})$) for the coefficient (β_1) that indicates treatment effect by the MMRM used for the primary analysis using the mRSS dataset prepared in Step #1.

Step #3: Repeat Step #1 and #2 for B times (B=1000 in this analysis) to obtain the t -statistics. Note that the t -statistics obtained in this procedure follow the empirical null distribution estimated by the actual dataset. Therefore, statistical test and inference are considered valid even if the sample size is small and longitudinal dataset is incomplete.

The p-value will be calculated as the following equation, where $T(\beta_1)$ is the t -statistics obtained by the original mRSS dataset:

$$p = \frac{1}{B+1} \left\{ 1 + \sum_{b=1}^B I\{|T^{(b)}(\beta_1^{null})| > |T(\beta_1)|\} \right\}$$

After calculating the 10% ($T_{0.1}(\beta_1^{null})$) and 90% ($T_{0.9}(\beta_1^{null})$) quantiles of the t -statistics obtained in Step #3, the 2-sided 80% CIs for β_1 will be β where the following equation holds:

$$T_{0.1}(\beta_1^{null}) \leq \frac{\hat{\beta}_1 - \beta}{\sqrt{Var(\hat{\beta}_1)}} \leq T_{0.9}(\beta_1^{null})$$

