5.4.2.3. Analysis Methods

For continuous endpoint as change from baseline in mRSS at Week 52, an MMRM model with treatment group, baseline mRSS, stratification factors (presence of ILD [yes, no] and baseline anti-topoisomerase I antibody status [positive, negative]), visit, treatment group by visit interaction, and baseline mRSS by visit interaction as fixed effects will be applied. The estimates of the treatment difference between guselkumab and placebo will be provided by the difference in the least squares means (LSMs), as well as the 2-sided 80% and 95% CIs for the differences and p-values.

For continuous endpoints other than change from baseline in mRSS at Week 52, an MMRM model with treatment group, baseline value of the endpoint, stratification factors (presence of ILD [yes, no], baseline mRSS (low [≥ 10 to ≤ 15], high [≥ 16 to ≤ 22]) and baseline anti-topoisomerase I antibody status [positive, negative]), visit, treatment group by visit interaction, and baseline value of the endpoint by visit interaction as fixed effects will be applied. The estimates of the treatment difference between guselkumab and placebo will be provided by the difference in the least squares means (LSMs), as well as the 2-sided 80% and 95% CIs for the differences and p-values. The degree of freedom will be calculated as the error degrees of freedom for the model minus the number of extra random effects estimated.

An unstructured covariance matrix for repeated measures within a participant will be used. In case of lack of convergence, empirical structured covariances will be used in the following order until convergence is reached: 1) Toeplitz 2) first order Autoregressive Moving Average. If the normality assumption is in question, an appropriate transformation will be used.

For binary endpoints such as proportion of participants achieving an ACR CRISS score of 0.6, a logistic regression model that includes factors for treatment group and stratification factors (presence of ILD [yes, no], baseline mRSS (low [≥ 10 to ≤ 15] or high [≥ 16 to ≤ 22]) and baseline anti-topoisomerase I antibody status [positive, negative]) will be applied provide the odds ratios, p-values, as well as the 2-sided 80% and 95% CIs for comparisons between guselkumab and placebo.

5.4.2.4. Supplementary Analysis for Change from Baseline in MRSS at Week 52

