5.5.2. Analysis Methods

The analyses of exploratory efficacy endpoints will be based on the FAS.

Descriptive statistics, such as n, mean, SD, median, IQ range, minimum and maximum for continuous variables and counts and percentages for discrete variables will be used to summarize data when applicable. The analysis will be based on the observed data; therefore, no imputation of missing data will be performed.

All statistical testing will be performed between treatment groups at the 2-sided 0.2 significance level.

Continuous efficacy endpoints collected at multiple post baseline time points (ie, the endpoints of change from baseline) will be compared using a MMRM model. The model will include all available data through Week 24 (for endpoints at Week 24) or through Week 52 (for endpoints at Week 52).

The explanatory variables of the MMRM model will include treatment group, baseline value of the endpoint, stratification factors (presence of ILD, baseline mRSS and baseline anti-topoisomerase I antibody status), visit, treatment group by visit interaction, and baseline value of the endpoint by visit interaction as fixed effects. The estimates of the treatment difference between treatment groups will be provided by the difference in LSMs. The 80% CI for the differences in LSMs will be calculated based on the MMRM.

The analysis of change from baseline in fibrotic change assessed with HRCT at Week 24 and nailfold capillaries change at Week 24 will be performed using ANCOVA (analysis of covariance) model with baseline value of the endpoint as covariate, and stratification factors (presence of ILD, baseline mRSS and baseline anti-topoisomerase I antibody status) and treatment group as factors.

A logistic regression model will be used to compare the proportion of participants achieving selected endpoints (eg, worsening of % predicted FVC) between guselkumab and placebo. The analyses will include treatment group, stratification factors (presence of ILD, baseline mRSS and baseline anti-topoisomerase I antibody status) as factors. The same intercurrent events and composite strategy defined in Section 5.4.2.2 will be applied to following endpoints as well:

- The proportion of participants who experience FVC decline compared with baseline through Week 52
- The proportion of participants who experience worsening of FVC through Week 52

A summary of baseline values and change from baseline at Week 24 and Week 52 will be presented for nailfold capillaroscopy.

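### The MMRM degrees-of-freedom rule counts records rather than participants, so p-values and CIs for the continuous endpoints come out slightly too favourable

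*SAP*

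**What the plan says.** SAP 5.3.3 fits an MMRM to change in mRSS with treatment, baseline mRSS, two stratification factors, visit, treatment by visit and baseline by visit as fixed effects, and an unstructured within-participant covariance. No random effect is named. The df rule is: "The degree of freedom will be calculated as the error degrees of freedom for the model minus the number of extra random effects estimated".

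SAP 5.4.2.3 repeats that sentence in the paragraph on continuous secondary endpoints other than mRSS at Week 52. The paragraph on mRSS at Week 52 has no df sentence. SAP 5.5.2 uses further MMRMs ("The 80% CI for the differences in LSMs will be calculated based on the MMRM") and gives no df rule.

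If the unstructured fit fails, "empirical structured covariances will be used in the following order until convergence is reached: 1) Toeplitz 2) first order Autoregressive Moving Average". SAP 5.4.2.3 has the same fallback.

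SAP 5.1.1 states that "95% CIs as well as 80% CIs will be provided for primary endpoint analysis and secondary endpoint analysis", as the reference for the internal GO/NO-GO decision.

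SAP 5.3.5 adds, as a sensitivity analysis of the primary result, a permutation method "considered to be more appropriate under small sample settings". From the quantiles of the t-statistics "obtained in Step #3, the 2-sided 80% CIs for" the treatment coefficient are then built. No 95% permutation interval is described.

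**The concern.** Repeated records on one participant are correlated and do not each add an independent piece of information about a treatment difference at one visit. That difference is between participants, so its standard error is estimated with roughly as many df as there are participants, less the between-participant parameters. A rule based on total records gives several times that number and uses a t reference that is too narrow. No small-sample correction of the standard error is named either.

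The primary success rule is p<0.2 (SAP 2), and the 80% and 95% CIs inform GO/NO-GO (SAP 5.1.1). A rule that errs only in the direction of an effect could tip a borderline result.

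**Working it through.** **1. The plan's own figure.** The documents print no df. The sample size reproduces: 2 × (1.2816 + 0.8416)² × (8/4.7)² = 26.1, rounded up to 27 per arm, 54 in total. SAP 3 then adds two ("Allowing for up to 2 participants randomized but without postbaseline efficacy assessments"), giving 56.

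**2. Degrees of freedom under the rule.** With no random effects, df = records − fixed-effect parameters. Visits come from Protocol 1.3, Table 1: mRSS and digital ulcers every 4 weeks (6 through Week 24, 13 through Week 52), HAQ-DI 4, lung function 3. With T visits the mRSS model has 1 (intercept) + 1 (treatment) + 1 (baseline) + 2 (strata) + 3(T − 1) parameters. The other endpoints have one more, for the mRSS stratum. The between-participant df is 56 − 5 = 51, or 56 − 6 = 50 with three strata.

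| Model, 56 complete participants | Records | Parameters | df by the rule | Between-participant df |
|---|---|---|---|---|
| mRSS, 6 visits | 336 | 20 | 316 | 51 |
| mRSS, 13 visits | 728 | 41 | 687 | 51 |
| Digital ulcers, 13 visits | 728 | 42 | 686 | 50 |
| HAQ-DI, 4 visits | 224 | 15 | 209 | 50 |
| FVC, DLCO, 3 visits | 168 | 12 | 156 | 50 |

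The rule's figures are maxima. With 54 participants the first row becomes 54 × 6 − 20 = 304 against 49.

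**3. Another reading of the rule.** If the extra random effects meant the unstructured covariance parameters (6 × 7/2 = 21, or 13 × 14/2 = 91), the rule would give 316 − 21 = 295, 687 − 91 = 596 and 686 − 91 = 595.

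**4. Effect of the df alone.** The true level is the two-sided tail, under the between-participant df, beyond the critical value that the rule uses.

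| df by the rule vs between-participant | Critical t, 80% CI | Critical t, 95% CI | True level at 0.20 | True level at 0.05 |
|---|---|---|---|---|
| 316 vs 51 | 1.2842 vs 1.2984 | 1.9675 vs 2.0076 | 0.2049 | 0.0546 |
| 687 vs 51 | 1.2828 vs 1.2984 | 1.9634 vs 2.0076 | 0.2054 | 0.0551 |
| 686 vs 50 | 1.2828 vs 1.2987 | 1.9634 vs 2.0086 | 0.2055 | 0.0552 |
| 295 vs 51 | 1.2844 vs 1.2984 | 1.9680 vs 2.0076 | 0.2048 | 0.0545 |

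For the first row, 1.2984/1.2842 = 1.011 and 2.0076/1.9675 = 1.020, so the intervals should be about 1% and 2% wider. At nominal 0.20, HAQ-DI gives 0.2045 and FVC/DLCO 0.2040.

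**5. Does Kenward-Roger give about 50 df and restore the level?** Null trials were simulated with 56 participants, normal outcomes, SD 8, AR(1) correlation 0.8, dropout completely at random and a REML unstructured fit. Correlation and dropout are assumptions.

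- Six visits, 4,000 trials each, dropout 0/10/20%: mean Kenward-Roger df 52.2/49.6/46.5. Level at 0.20 under the SAP rule 0.207/0.194/0.209, under Kenward-Roger 0.201/0.184/0.198 (Monte Carlo SE 0.006).
- Thirteen visits: mean Kenward-Roger df 52.8 with complete data and 47.5 at 15% dropout.
- Thirteen visits with slower-decaying correlation, 0.8 × 0.95^(lag−1): 0.206 then 0.200 with complete data (3,000 trials, SE 0.007). With an assumed 25% dropout, 0.216 then 0.202 (3,688 trials, SE 0.007), and at nominal 0.05, 0.063 then 0.049.

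Monte Carlo error in each level is about as large as the effect. Both methods were applied to the same simulated trials, though, and the SAP rule rejected more often in every setting.

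**The case against.** The best defence is that the effect is about half a percentage point at a 20% level, and the formal success criterion already has a small-sample check in the permutation analysis. The secondary p-values are nominal, multiplicity is not controlled, and no CI threshold is stated. All of this is true and keeps the point minor. It does not remove it: the permutation analysis is a sensitivity analysis, and it leaves the primary 95% CI and the intervals of the continuous secondary endpoints without a check.

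A reader might infer more than the documents support:

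- *All secondary intervals are affected.* They are not. Worsening of mRSS and ACR CRISS response are analysed by logistic regression, where this rule plays no part.
- *The primary analysis certainly has 316 df, or certainly 687.* SAP 5.3.3 does not say whether the primary model stops at Week 24. Likewise 687 for mRSS at Week 52 holds only if the same rule is meant there.
- *The level is materially inflated.* The largest unstructured-fit figures need 25% missing data. The documents give no dropout rate, and the two participants allowed for in SAP 3 are those with no post-baseline data. The composite strategy also supplies zeros, not missing values, after its intercurrent events, which the simulations did not model.
- *The fallback would badly distort the level.* The chance of non-convergence is unknown, and large distortions appear only under assumed patterns of SD across visits. What stands is that *empirical* is undefined, and model-based and sandwich standard errors are different analyses.

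**Conclusion.** The df rule is wrong as written for an MMRM without random effects. It gives 156 to 687 df, depending on endpoint and visits, where the treatment contrast carries about 50-51. Counting covariance parameters as random effects would not rescue it. From the df alone, the true level is about 0.205 at nominal 0.20 and 0.055 at 0.05, and the 80% and 95% CIs are about 1% and 2% too narrow, always towards finding an effect. These sizes assume 56 participants with complete data; the shortfall is somewhat larger if many data are missing. Only a borderline result would change. The affected results are the primary p-value and CIs and those of FVC, DLCO, digital ulcers and HAQ-DI, plus mRSS at Week 52 if the rule carries over. Severity: minor.

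**What to change.** In SAP 5.3.3 and 5.4.2.3 replace the df sentence with: *Standard errors and denominator degrees of freedom will use the Kenward-Roger method.* State that this also covers mRSS at Week 52, and apply it to the MMRMs in 5.5.2. State in 5.3.3 which visits enter the primary model. Keep the permutation analysis.

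For the non-convergence fallback, state whether *empirical* means sandwich standard errors. If it does, name a small-sample correction and a participant-based df (participants minus 5 for mRSS, minus 6 for the other endpoints), because Kenward-Roger applies to model-based standard errors.

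The cost is a few sentences across three sections. No data collection, sample size or estimand changes. CIs become about 1-2% wider with near-complete data: in simulation 1.3% and 2.2% (80% and 95%) at 6 visits, and 1.5% and 2.5% at 13. With 13 visits and an assumed 25% dropout the figures were 3.7% and 4.9%.

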1.3. Schedule of Activities (SoA)

Table 1: Schedule of Activities (SoA) of Screening and Double-Blind Study Intervention (Main Study)

Period	Screening	Double-blind Study Intervention														Safety Follow-up (EOS) °	Early Termination Visit (ET)
Week ^h	-6 to 0	0	4	8	12	16	20	24	28	32	36	40	44	48	52 ⁿ	60	
Study Procedure																	
Screening/Administrative																	
ICF ^a	X																
ICF for optional genetic research	X																
samples																	
ICF for participation of LTE ^p														(X)			
Medical history and demographics	X																
Inclusion/exclusion criteria ^b	X	X															
Study Intervention																	
Administration																	
Randomization		X															
Administer study intervention		X	X	X	X	X	X	X	X	X	X	X	X	X			
Efficacy Assessments ^c																	
mRSS ^g	X	X	X	X	X	X	X	X	X	X	X	X	X	X	X		X
Physician's global assessment		X			X			X			X				X		X
Digital ulcer assessment	X	X	X	X	X	X	X	X	X	X	X	X	X	X	X		X
Patient's global assessment		X			X			X			X				X		X
HAQ-DI		X			X			X			X				X		X
FSSG		X			X			X			X				X		X
Nailfold capillaroscopy		X						X							X		X
Lung HRCT (centrally read) ¹	X							X							X		
Pulmonary function tests ⁱ	X				X			X							X		X
ACR CRISS ^m	X				X			X							X		X
Safety Assessments																	
Physical examination	X	X	X	X	X	X	X	X	X	X	X	X	X	X	X	X	X
Height	X																
Weight	X				X			X							X		X
Vital signs	X	X	X	X	X	X	X	X	X	X	X	X	X	X	X	X	X
Tuberculosis evaluation ^k	X	X	X	X	X	X	X	X	X	X	X	X	X	X	X	X	X
12-lead ECG	X							X							X		X
Urine pregnancy test	X	X	X	X	X	X	X	X	X	X	X	X	X	X	X	X	X

 $CONFIDENTIAL-FOIA\ Exemptions\ Apply\ in\ U.S.$

Period	Screening	Screening Double-blind Study Intervention														Safety Follow-up (EOS) °	Early Termination Visit (ET)
Week ^h	-6 to 0	0	4	8	12	16	20	24	28	32	36	40	44	48	52 ⁿ	60	
Study Procedure																	
Chest radiograph	X																
Concomitant therapy	X	X	X	X	X	X	X	X	X	X	X	X	X	X	X	X	X
Adverse Events	X	X	X	X	X	X	X	X	X	X	X	X	X	X	X	X	X
Clinical Laboratory Tests																	
IGRA (QuantiFERON- TB test or T-SPOT)	X																
Hepatitis B and C serologye	X																
HIV antibody test	X																
Hematology	X	X	X	X	X	X	X	X	X	X	X	X	X	X	X	X	X
Chemistry including CRP	X	X	X	X	X	X	X	X	X	X	X	X	X	X	X	X	X
Urinalysis	X	X	X	X	X	X	X	X	X	X	X	X	X	X	X	X	X
Autoantibodies (including, but not limited to anti-RNA polymerase, anti-centromere, and anti-topoisomerase)	X																

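### The fallback covariance structures assume one variance at all visits, so if the unstructured MMRM does not converge, the model-based Week 24 and Week 52 standard errors can be too small or too large

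*SAP*

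**What the plan says.** For the primary analysis, SAP 5.3.3 begins with the right structure: "An unstructured covariance matrix for repeated measures within a participant will be used". If that does not converge, "empirical structured covariances will be used in the following order until convergence is reached: 1) Toeplitz 2) first order Autoregressive Moving Average". SAP 5.4.2.3 repeats both sentences for the Week 52 mRSS change and the other continuous secondary endpoints. No heterogeneous version of either fallback is listed, and *empirical* is not defined.

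The same section sets the degrees of freedom: "The degree of freedom will be calculated as the error degrees of freedom for the model minus the number of extra random effects estimated". It names no small-sample correction to the standard error. On the level of the test, SAP 5.1.1 says "a 2-sided alpha of 0.2 is allocated for all hypothesis testing throughout the study", and it makes the 80% and 95% intervals the reference for the internal go/no-go decision.

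The data window of the model is given only for the exploratory endpoints (SAP 5.5.2). Neither 5.3.3 nor 5.4.2.3 says whether the Week 24 comparison comes from a model of visits through Week 24 or through Week 52.

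**The concern.** An unstructured matrix gives every visit its own variance. Toeplitz and first-order ARMA, as named, give all visits the same one. The primary test concerns one visit, Week 24, and the Week 52 secondary test concerns another. Under a common variance, the model-based standard error at each of these visits reflects an average over all modelled visits.

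The outcome is change from baseline, which is zero by construction at Week 0. Some growth in its spread over the early visits is therefore a reasonable expectation, although the documents do not show it. If the tested visit is more variable than average, the p-value is too small and the intervals too narrow. If it is less variable than average, power is lost. The proof-of-concept criterion is a p-value below 0.2, so either error bears on the decision.

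**Working it through.** **Inputs from the documents.** Two-sided alpha 0.20, SD 8, difference 4.7, 1:1 allocation (SAP 3 and 5.1.1). mRSS every 4 weeks (Protocol Table 1), so 6 post-baseline visits through Week 24 and 13 through Week 52. **Assumed:** the SD of change at each visit, because only the single planning SD of 8 is given.

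**1. The plan's own figure.** n per arm = 2 × (1.2816 + 0.8416)² × (8/4.7)² = 26.1, rounded up to 27, or 54 in total. This reproduces the stated 54; 56 are planned.

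**2. How likely the trigger is.** An unstructured matrix for k visits has k(k+1)/2 parameters: 6 × 7/2 = 21 through Week 24, and 13 × 14/2 = 91 through Week 52. With about 56 participants, non-convergence is most plausible in a 13-visit model. Among the secondary endpoints, mRSS and digital ulcer counts have 13 visits. Lung function has 3 (Weeks 12, 24, 52) and HAQ-DI has 4 (Weeks 12, 24, 36, 52).

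**3. Size of the mis-scaling, model-based standard error.**
- Ratio = √(mean of the visit variances) / SD at the tested visit.
- Realised type I error = 2 × [1 − Φ(1.2816 × ratio)].

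Worked case, SD 4 to 8 in equal steps over six visits (4, 4.8, 5.6, 6.4, 7.2, 8): mean variance = 227.2/6 = 37.87, root 6.15, ratio 6.15/8 = 0.77. Type I error = 2 × [1 − Φ(0.986)] = 0.32, so an 80% interval covers about 68%.

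| Assumed SD path | Visits modelled | Tested | Ratio | Type I error |
|---|---|---|---|---|
| Flat | any | either | 1.00 | 0.20 |
| 6 to 8 | to Week 24 | Week 24 | 0.88 | 0.26 |
| 4 to 8 | to Week 24 | Week 24 | 0.77 | 0.32 |
| 3 to 8 | to Week 24 | Week 24 | 0.72 | 0.36 |
| 6 to 8 | to Week 52 | Week 24 | 1.03 | 0.19 |
| 6 to 8 | to Week 52 | Week 52 | 0.88 | 0.26 |
| 4 to 8 | to Week 52 | Week 24 | 1.08 | 0.17 |
| 4 to 8 | to Week 52 | Week 52 | 0.77 | 0.33 |

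For the 4-to-8 path through Week 52, the SD at Week 24 is 4 + 4 × 20/48 = 5.67 and the root mean variance is 6.13. The ratios are therefore 6.13/5.67 = 1.08 and 6.13/8 = 0.77.

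**4. Check by fitting the structures.** Homogeneous Toeplitz and ARMA(1,1) were fitted by likelihood to assumed covariances (autoregressive 0.9 or exchangeable 0.7). Two further paths, both modelled through Week 52, were added:
- SD rising from 4 to 8 by Week 24 and then level: ratio 0.86 to 0.89 at both weeks (type I error 0.26 to 0.27).
- SD 5 to 8 at Week 24, then falling to 6: Week 24 ratio 0.79 to 0.85, Week 52 ratio 1.06 to 1.13.

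**5. If *empirical* means a sandwich standard error.** The simulation used 27 per arm, complete data and 1,200 runs per scenario (Monte Carlo error about 0.012). The Week 52-window runs used ARMA only.
- SD 4 to 8 through Week 24: the ratio rises from 0.76–0.77 to 0.92–0.93, and type I error falls from about 0.33 to 0.24–0.25.
- Week 52, same SDs over 13 visits: the ratio rises from 0.78 to 0.96, and type I error falls from 0.34 to 0.22.
- All simulated scenarios: sandwich ratio 0.92 to 1.00, type I error 0.21 to 0.25. Under a flat SD the ratio is still 0.94 to 0.96, so most of what remains is small-sample bias of the sandwich.
- A regression at the tested visit alone, standing in for a fit with visit-specific variances: type I error 0.18 to 0.22 throughout.

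**The case against.** A reader might infer that the fallback would understate both the Week 24 and the Week 52 standard errors, and that the primary test would then run at about 0.32 instead of 0.20. The documents do not support that, for four reasons.

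- **The variance path is unknown.** A flat SD does no harm. The composite rule (SAP 5.3.2, extended to rescue after Week 24 in 5.4.2.2) sets change to zero after an intercurrent event, which could flatten or reverse any rise.
- **The direction depends on an unstated window.** The current plan has no Week 24 database lock, so Week 52 data will exist when the primary analysis is run. If those visits enter the model and SD rises steadily, the Week 24 standard error is too large.
- ***Empirical* may already mean a sandwich estimator.** That is plausible in a SAP that names SAS procedures, and it removes most of the distortion. Nor is such a standard error incompatible with the stated degrees of freedom: an error-df count does not depend on which standard error is used.
- **The primary endpoint has a backstop.** The permutation analysis in SAP 5.3.5 refers the same t-statistic to its own permutation distribution, so a mis-scaled denominator largely cancels.

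All four stand, and they limit the claim. They do not remove it. The permutation result is a robustness check, not the criterion. No equivalent is planned for Week 52: the supplementary analysis in 5.4.2.4 changes only the handling of rescue and uses a similar MMRM. It is fair to add that Week 52 p-values are nominal.

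**Conclusion.** The point holds as a conditional weakness. On non-convergence, both named fallbacks impose equal variance across visits. If the variance of mRSS change varies by visit, the model-based standard error at Week 24 or Week 52 can err in either direction. Over the assumed rises to SD 8, type I error at nominal 0.20 is 0.26 to 0.36 at the last visit of a six-visit model. With a 13-visit window and SD rising from 4 or 6 to 8, it is 0.17 to 0.19 at Week 24 and 0.26 to 0.33 at Week 52. A sandwich reading brings it to about 0.21 to 0.25.

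These figures illustrate a range and are not an expected effect. They rest on assumed SD paths and on the fallback being used at all, which is most plausible in a 13-visit model. The exposure is greatest at Week 52, where no permutation check is planned.

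**What to change.** In SAP 5.3.3 and 5.4.2.3:

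1. After the unstructured matrix, list heterogeneous Toeplitz, then heterogeneous first-order autoregressive, ahead of the current structures.
2. Keep homogeneous Toeplitz and ARMA(1,1) only as a last resort, with a sandwich standard error and a named small-sample correction. State that this is what *empirical* means. Simply deleting the word could remove protection the authors intended.
3. If Kenward-Roger is adopted for the model-based heterogeneous fits, amend the error-degrees-of-freedom sentence to match.
4. State that the Week 24 primary model uses data through Week 24.

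The cost is SAP wording and a few more variance parameters in a fallback model. Heterogeneous Toeplitz has k variances and k − 1 correlations against k parameters for the homogeneous form. That adds 5 at six visits (11 against 6) and 12 at thirteen (25 against 13, still far below 91).
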